11.4 Sample Size Considerations

Sample size for this pilot study is primarily driven by patient availability and larger, multi-center randomized trials will likely be needed to fully demonstrate efficacy. However, for the primary objective, a sample size of 20 patients (of which we expect 25% having stable disease, 50% partial responders, and 25% complete responders) will provide 80% power to detect a 0.76 standard deviation difference in CEUS measurement means (e.g., mean contrast perfusion time) between mRECIST response levels, by analysis of variance (ANOVA) with a nominal 5% type I error rate. Similarly, in analyses comparing the prospective treated patients to matched historical control patients, 20 patients per arm will provide 80% power to detect a relative effect size of 0.66 standard deviations by t-test with a nominal 5% type I error rate (i.e., a moderately large, but reasonable effect given our current data in HCC patients).

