11.2 Analysis Plans

In general, categorical data will be summarized as counts and percentages (or proportions) and continuous data will be summarized with descriptive statistics such as mean, standard deviation (SD), median, and range. All statistical analysis will be performed by [name] using SAS version 9.4 (Cary, NC). All statistical tests will be conducted at a nominal $\alpha=0.05$ level. For H1 (see Section 11.1 above), the respective relationships between the CEUS-derived contrast reperfusion time, degree of tumor enhancement relative to the surrounding parenchyma, tumoral IFP and 3D morphological features of the vasculature with the patients' subsequent mRECIST diagnosis (3 levels: stable disease, partial response, or complete response) will be evaluated by testing for mean difference in the CEUS measures between response levels by analysis of variance (ANOVA). Historical controls ($n=20$) will be identified from a pool of recently treated non-HCC patients at Jefferson that meet study eligibility criteria for the study and match our enrollees by propensity score based on a logistic regression model including patient age, tumor size, bilirubin and ECOG performance score and utilizing a greedy matching algorithm. Testing for the effect of radioembolization on tumor response in H2 will be conducted using non-parametric Mann-Whitney U-tests of the differences in mRECIST distributions between historical controls and enrolled patients. The difference in time-to-event endpoints (i.e., to next treatment or death, respectively) between the treated and historical control patients for H3 will be estimated and tested using Kaplan-Meier survival methods and log-rank tests. Differences in safety data will be evaluated for H4 with descriptive statistics, but not statistical hypothesis tests. A similar ANOVA approach taken for evaluating H1 will be taken for evaluating the means of CEUS measures at different times (2-4 hours, 1 week, and 2 week, respectively) of tumor perfusion and residual vascularity values between response levels to address H5 and SHAPE IFP values for addressing H8, as well as the means of changes from baseline in these measure for addressing H6 and H9. The agreement on response between mRECIST response diagnoses at 1 month and 3-6 months post-TARE will be tested using McNemar's test.

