11.4.1 Replacement Policy

Subjects that withdraw from the study will not be replaced. If a sufficiently high number of subjects withdraw, the protocol will be amended to allow for greater enrollment.

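### Section 11.4 claims 80% power for a 0.76 SD difference in CEUS means, but 0.76 matches Cohen's f; read literally, a 0.76 SD difference gives 15% to 63% power depending on the pattern of means

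*Combined protocol and SAP*

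**What the plan says.** Section 11.4 of the combined protocol and SAP bases its power statement on 20 patients, "of which we expect 25% having stable disease, 50% partial responders, and 25% complete responders". With that split it says the study "will provide 80% power to detect a 0.76 standard deviation difference in CEUS measurement means", and the sentence goes on to specify the comparison as "between mRECIST response levels, by analysis of variance (ANOVA) with a nominal 5% type I error rate". It offers mean contrast perfusion time as an example of such a measurement. It names no effect-size index and assumes no pattern for the three means.

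Section 11.2 confirms the test: a comparison of mean CEUS measures across three response levels by one-way ANOVA. It also fixes the level: "All statistical tests will be conducted at a nominal $\alpha=0.05$ level".

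Two further statements bear on the point. Section 11.4 opens with "Sample size for this pilot study is primarily driven by patient availability", and Section 11.4.1 adds "Subjects that withdraw from the study will not be replaced".

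**The concern.** A reader will take a difference of 0.76 SD in means between response levels as a gap between groups, for example between complete responders and patients with stable disease. With only 5, 10 and 5 patients per group, 80% power for a gap of that size is not plausible. With three groups, a single difference does not even determine the power until the position of the third mean is given.

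This sentence is the only place where the documents say what the primary analysis can detect. If the number is really a different index, a non-significant ANOVA could be misread as evidence against gaps of about 0.76 SD that the study had little chance of finding. Anyone reusing the figure to plan later work on CEUS prediction would start from a detectable gap that is too small.

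**Working it through.** **Inputs, all from the document.** N = 20 and the 25/50/25% split (Section 11.4) give n = 5 (stable disease), 10 (partial response) and 5 (complete response). There are three levels (Section 11.2) and alpha is 0.05 (Sections 11.2 and 11.4). The test is the one-way ANOVA F test with 2 and 17 degrees of freedom.

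**Formulas.** Write the group means μᵢ in units of the within-group SD, and let μ̄ = Σnᵢμᵢ/N. Then λ = Σnᵢ(μᵢ − μ̄)², Cohen's f = √(λ/N), and power is the probability that a noncentral F(2, 17, λ) variable exceeds the 5% critical value of the central F(2, 17).

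**Step 1: reproduce the plan's figure.** 80% power requires λ = 11.554, so f = √(11.554/20) = 0.760. In the other direction, f = 0.76 gives λ = 20 × 0.76² = 11.552 and power 0.7999. The plan's 80% and 0.76 therefore agree exactly when 0.76 is Cohen's f.

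**Step 2: read 0.76 as a difference between means.** Means are listed in the order stable disease, partial response, complete response.

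| Pattern | Means | λ | Power | N for 80% at 1:2:1 |
|---|---|---|---|---|
| Evenly spaced, full range 0.76 | 0, 0.38, 0.76 | 1.444 | 15.2% | 140 |
| One end group differs | 0, 0, 0.76 | 2.166 | 20.8% | 96 |
| Partial response differs from both ends | 0, 0.76, 0 | 2.888 | 26.6% | 72 |
| Each adjacent step 0.76, in response order | 0, 0.76, 1.52 | 5.776 | 49.0% | 40 |
| Steps of 0.76, partial response at the extreme | 0, 1.52, 0.76 | 7.942 | 63.1% | 28 |

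Example for the third row: μ̄ = 10 × 0.76/20 = 0.38, so λ = 20 × 0.38² = 2.888. The last column is for scale only and was searched in multiples of 4. A simulation with 40,000 replicates per pattern agreed with all five powers to within 0.4 percentage points.

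**Step 3: ceiling when 0.76 is the largest gap.** λ is convex in the means, so with all means inside an interval of width 0.76 it is largest when every group sits at one end or the other. The possible splits are 5 against 15, with λ = 0.76² × 5 × 15/20 = 2.166, and 10 against 10, with λ = 0.76² × 10 × 10/20 = 2.888. The ceiling is therefore 26.6%, and a grid search over the middle mean confirmed it.

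**Step 4: gap that does give 80% power.** Set λ = 11.554 and solve for the gap d between the most separated levels.

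- Evenly spaced: λ = 2 × 5 × (d/2)² = 2.5d², so d = √(11.554/2.5) = 2.15 SD. The adjacent step is 1.07 SD. These are 2.8 and 1.4 times 0.76.
- One end group differs: λ = d² × 5 × 15/20 = 3.75d², so d = 1.76 SD, 2.3 times 0.76.
- Partial response differs from both ends: λ = d² × 10 × 10/20 = 5d², so d = 1.52 SD, 2.0 times 0.76.

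**Step 5: other readings tried.** With 0.76 as a difference in means, equal group sizes give 19% to 62%, alpha 0.10 gives 25% to 63% on the patterns run, and pairwise t-tests within the 20 patients (one- or two-sided) give 19% to 50%. Taking 0.76 as the unweighted SD of the three means gives 49% to 85%, depending on the pattern. None of these settles on 80%.

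**The case against.** The strongest reply is that the sponsor's calculation is correct and only its label is loose: f is itself expressed in within-group SD units, and the 80% is sound for f = 0.76. That is true, and it is why neither the sample size nor the test needs to change. It does not rescue the sentence, which speaks of a difference in means between response levels. The next sentence of Section 11.4 gives a t-test effect of 0.66 SD, which is a difference between two means, and so invites the reader to treat 0.76 as the same kind of quantity.

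Second, the span of 15% to 63% covers two readings. This is fair, and they should be kept apart: 15% to 27% if 0.76 is the largest gap, and 49% or 63% if it is the smallest. The 63% also requires a non-monotone pattern, with partial response at an extreme. Neither reading reaches 80%.

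Third, this is an availability-driven pilot, and the larger trials that Section 11.4 mentions are about efficacy, so they would not naturally be sized on this ANOVA. That stands in part: the risk to future planning is indirect. The risk of misreading this study's own primary result remains.

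Finally, the documents do not say that 0.76 is Cohen's f. That is inferred from the numerical match. The statement that 20 patients split 5/10/5 give 80% power at f = 0.76 is nevertheless true of this design, wherever the number came from.

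**Conclusion.** The concern holds. As worded, the power statement for the primary objective is wrong: no ordinary reading of a 0.76 SD difference in means gives 80%. Power is at most 27% if 0.76 is the largest gap, and 49% for steps of 0.76 in response order. The gap between the most separated levels that gives 80% power is 1.52 to 2.15 SD across the three patterns solved above, two to nearly three times the stated figure.

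The results assume normal data with a common within-group SD, an actual split of 5/10/5, and all 20 patients evaluable. The last is not assured, because withdrawals are not replaced. The consequence is limited to how the study's sensitivity is described, since N was set by availability. The sentence should be corrected, but it does not undermine the design.

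**What to change.** Replace the sentence in Section 11.4 with one to this effect:

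> With 20 evaluable patients (5 stable disease, 10 partial response, 5 complete response), one-way ANOVA at the 5% level has 80% power for Cohen's f = 0.76. This corresponds to 1.07 SD between adjacent response levels (2.15 SD between stable disease and complete response) if means are evenly spaced, 1.76 SD if one end group differs from the other two, or 1.52 SD if partial response differs from both.

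The authors should confirm that f was the index used. If they prefer to present a single pattern, they should name it and justify it. The word evaluable matters because Section 11.4.1 does not replace withdrawals, and the 80% needs all 20 patients.

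The cost is one sentence of protocol wording and a less favourable stated detectable difference. N, the ANOVA and alpha stay as they are.

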A meta-analysis of 12 studies in which 298 patients suffering ICC were treated with Yttrium-90 (Y-90) radioembolization reported overall median survival of 15.5 months⁶. TARE can be offered to patients with adequate performance status according to Eastern Cooperation Oncology Group (ECOG) performance score, blood cell count, liver function, and kidney function⁴. Additionally, TARE is being increasingly used for the treatment of other non-HCC solid tumors in the liver including colorectal cancer metastasis, uveal melanoma metastasis, and neuroendocrine metastasis. Using this approach, radioactive microspheres are delivered via a catheter placed in the hepatic artery branch supplying the tumor, thereby providing a localized and sustained release of radiation. The microspheres used are 20-30 μ m diameter glass beads containing Y-90. Y-90 is a pure beta emitter. It decays to stable Zirconium-90 with a half-life of 64 hours and has an average energy emission of 0.94 MeV. The maximum tissue penetration in the liver is 10 mm^{7,8,9}. Lobar doses range from 110-150 Gy, but radiation delivered to malignant tissue is dependent on distance from the yttrium source. Consequently, treatment response after radioembolization is between 25-60% when based on modified response criteria in solid tumors (mRECIST)^{9,6,10}.

Ultrasound contrast agents

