2.1.2 Secondary

- To characterize the safety and preliminary efficacy of using localized UCA inertial cavitation to improve tumoral response to radioembolization.
- To determine if CEUS estimated tumor perfusion and residual vascularity 7-14 days post treatment can predict tumoral response to radioembolization.
- To evaluate tumoral response using the patient's 1 month MRI (obtained clinically) and determine the accuracy of MR or CT tumor evaluation at this earlier time point.

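### The stated 80% power at 0.66 SD with 20 per arm does not apply to the planned unpaired comparison with historical controls: power is about 53%, and 80% needs about 0.91 SD

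*Combined protocol and SAP*

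**What the plan says.** Section 11.4 gives two power statements. The one at issue covers the comparison of enrolled patients with matched historical controls: "20 patients per arm will provide 80% power to detect a relative effect size of 0.66 standard deviations by t-test", at a nominal 5% type I error. It describes this effect as fairly large but plausible in view of the group's HCC data. It does not say whether the t-test is paired or two-sample, one- or two-sided, or whether the SD is that of the outcome or of within-pair differences.

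Section 11.2 sets out how that comparison will be made. "Historical controls ($n=20$) will be identified from a pool of recently treated non-HCC patients at Jefferson" and matched to enrollees by propensity score with a greedy algorithm. Tumor response (H2) is then compared by "non-parametric Mann-Whitney U-tests of the differences in mRECIST distributions between historical controls and enrolled patients". Time to next treatment and survival (H3) are compared by Kaplan-Meier and log-rank methods. Safety (H4) is descriptive. No analysis against the controls uses the pairs.

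The comparison serves the secondary objective in section 2.1.2: "To characterize the safety and preliminary efficacy of using localized UCA inertial cavitation to improve tumoral response to radioembolization".

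**The concern.** The phrase "20 patients per arm will provide 80% power" reads as a two-group calculation, and every test planned against the controls is a two-group test. For two independent groups of 20, an effect of 0.66 SD is too small to be detected with 80% power.

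If the effect the protocol regards as plausible were real, an unpaired t-test would miss it about 47% of the time (100 − 53), against the stated 20%. A null H2 result could then be read as evidence against an effect that the study had little better than an even chance of finding. Section 11.4 expects larger randomized trials to follow, and their planners could take 0.66 SD as detectable with 20 per arm.

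**Working it through.** **Inputs.** 20 enrolled and 20 controls (sections 11.2 and 11.4); effect 0.66 SD, power 80%, type I error 5% (section 11.4). Sidedness is not stated, so two-sided is taken as the main case and one-sided is also shown. Power is from the noncentral t distribution.

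**1. Reproducing the plan's figure.** A paired t-test on n = 20 pairs has df = 19 and noncentrality d × √n = 0.66 × √20 = 2.95.
- Two-sided 5% power is 79.9%, and 80% is reached at d = 0.660.
- This matches the stated figure, with d in SDs of within-pair differences. That a paired formula was used is an inference from the match; the text does not say so.

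**2. Unpaired t-test, 20 per arm.** Here df = 38 and noncentrality is d × √(n/2) = 0.66 × √10 = 2.09.

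| Version | Power at 0.66 SD | Effect for 80% power | n per arm for 80% at 0.66 SD |
|---|---|---|---|
| t, two-sided 5% | 53.0% | 0.909 SD | 38 |
| t, one-sided 5% | 65.7% | 0.801 SD | 30 |
| Normal approximation, two-sided 5% | 55.1% | 0.886 SD | 37 |

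The normal approximation can be checked by hand: (1.960 + 0.842) × √(2/20) = 0.886. With the t-test, 38 per arm gives 81.0%. No unpaired version at 5% reaches 80%; even a two-sided 20% level gives only 78.4%.

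**3. A paired test with 0.66 in outcome SDs.** The effect in SDs of differences is 0.66/√(2(1 − ρ)), where ρ is the within-pair correlation. Power with 20 pairs is:

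| ρ | 0 | 0.2 | 0.3 | 0.4 | 0.5 |
|---|---|---|---|---|---|
| Power | 51% | 60% | 66% | 73% | 80% |

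So 80% requires ρ of about 0.5. The protocol states no correlation.

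**4. The test planned for H2.** Mann-Whitney power was simulated on the three mRECIST levels (stable, partial, complete), with 20 per arm, 40,000 simulations, a tie-corrected normal approximation and a null rejection rate of 4.8%. The enrolled group was set at 25/50/25%, the split that section 11.4 expects.
- Latent-normal shift of 0.66 (controls 49/41/9%): 44%.
- Difference of 0.66 SD on a 0/1/2 score (controls 52/40/8%): 52%.

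Section 1.1 says "treatment response after radioembolization is between 25-60% when based on modified response criteria in solid tumors". Taking that range for the controls, and assuming a PR:CR ratio of 2:1 that the documents do not give:

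| Control response | 60% | 50% | 40% | 30% | 25% |
|---|---|---|---|---|---|
| Mann-Whitney power | 14% | 32% | 56% | 79% | 88% |

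With PR:CR of 1:1 the end points are 8% and 83%; with 4:1 they are 24% and 92%.

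**The case against.** The strongest reply is that nothing was miscalculated. Section 11.4 speaks of matched controls, section 11.2 describes 20 controls matched to 20 enrollees, and 0.66 is the correct paired result for 20 pairs. This stands as an account of where the number probably came from, and it means the fault is better described as a mismatch between sections 11.4 and 11.2 than as a slip in a sum. It does not rescue the statement. Matching is used only to select the controls, the planned tests ignore the pairs, and the SD of differences is neither defined nor tied to a correlation.

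A second reply is that little depends on the figure. Section 11.4 says the sample size is driven mainly by patient availability and that larger trials will likely be needed; no decision rule uses 0.66. That is fair, and it limits the weight of the point. The 47% miss rate also describes a t-test, which is not the test planned for H2 or H3. The ordinal Mann-Whitney figures at a comparable effect are similar or somewhat worse.

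A third reply is that the table by control response rests on a literature range that is not a forecast for these matched controls, on an assumed PR:CR ratio, and on a response split that the protocol gives for a different analysis. This also stands. The table shows how widely power varies, and the conclusion does not depend on it.

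**Conclusion.** The concern holds. The stated 80% power at 0.66 SD is not a property of the unpaired comparison that section 11.2 plans. With 20 per arm at two-sided 5%, t-test power at 0.66 SD is 53%, 80% power needs 0.91 SD, and 80% power at 0.66 SD would need 38 per arm. A one-sided reading (66%; 0.80 SD) does not change the conclusion. Mann-Whitney on three levels gives about 44% to 52% at an effect of similar size, depending on how 0.66 is translated to the ordinal scale.

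The t-test figures assume equal-variance normal outcomes and all 20 patients evaluable in each group. Withdrawals are not replaced (section 11.4.1), so fewer may be available unless enrollment is extended by amendment.

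This should be corrected, but its reach is modest: it concerns a secondary, preliminary comparison in a pilot. The separate power statement for the primary objective is outside this point and was not assessed here.

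**What to change.** Choose one of two routes.

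1. **Keep the unpaired analyses.** In section 11.4, restate the detectable effect as about 0.91 SD at 80% power, or about 53% power at 0.66 SD, for a two-sided 5% test with 20 per arm. Say that power of the ordinal Mann-Whitney test is somewhat lower. If power is quoted for particular response rates, show a range with its assumptions (about 14% to 88% under the 2:1 assumption above), not one figure. Report the H2 difference in response with a 95% confidence interval and label it preliminary. As an illustration, 15/20 against 10/20 is a difference of 25 points, with a Newcombe interval for independent groups of about −5 to 49.
2. **Adopt pairing.** Define 0.66 as SDs of within-pair differences, state the assumed within-pair correlation (about 0.5 if 0.66 is meant in outcome SDs), and plan a matched-pair test in section 11.2. Note that three ordinal levels will give many zero differences.

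The cost is wording in section 11.4, and in section 11.2 if pairing is chosen. No extra patients are needed. On the first route the stated figure becomes less favourable.

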11.4.1 Replacement Policy

Subjects that withdraw from the study will not be replaced. If a sufficiently high number of subjects withdraw, the protocol will be amended to allow for greater enrollment.

11.4.2 Accrual Estimates

We estimate it will take 2 years to recruit 20 subjects for this trial.

11.5 Exploratory Analysis

Exploratory analysis is anticipated for the associations between IFP or reductions in IFP and mRECIST response. The plans for that analysis are included in the statistical analysis plans above.

11.6 Evaluation of Safety

The investigator is responsible for the detection and documentation of events meeting the criteria and definition of an AE or SAE. Each patient will be instructed to contact the investigator immediately should they manifest any signs or symptoms they perceive as serious.

To determine the safety profile of the treatment the following safety assessments will be done:

- Clinical laboratory tests
- Physical examinations
- Sitting vital signs, body temperature and body weight
- Adverse events registration with attribution in accordance with section 8.3.1

The methods for collection safety data are described below.

Expected AE's for the SoC TARE and the ultrasound contrast agent (i.e., Optison) will be recorded.

12 Source Documents and Access to Source Data/Documents

Study staff will maintain appropriate medical and research records for this study, in compliance with ICH E6, and regulatory and institutional requirements for the protection of confidentiality of participant information. Study staff will permit authorized representatives of SKCC and regulatory agencies to examine (and when required by applicable law, to copy) research records for the purposes of quality assurance reviews, audits, and evaluation of the study safety, progress and data validity.

Source Data

The medical records for each patient should contain information which is important for the patient's safety and continued care and to fulfil the requirement that critical study data should be verifiable. To achieve this, the medical records of each patient should clearly describe at least:

- That the patient is participating in the study e.g., by including the enrollment number and the study code or other study identification;
- Date when Informed Consent was obtained from the patient for the following and statement that patient received a copy of the signed and dated Informed Consent;
- Results of all assessments confirming a patient's eligibility for the study;
- Diseases (past and current; both the disease studied and others, as relevant);
- Surgical history, as relevant;
- Treatments withdrawn/withheld due to participation in the study;
- Results of all assessments performed during the study;
- WHO performance status assessments conducted as part of the study;
- Treatments given, changes in treatments during the study and the time points for the changes;
- Visits to the clinic during the study, including those for study purposes only;
- AEs and SAEs (if any) including causality assessments;
- Date of, and reason for, discontinuation from study treatment;
- Date of, and reason for, withdrawal from study;
- Date of death and cause of death, if available;
- Additional information according to local regulations and practice.

Source Data Verification

The investigator will be visited on a regular basis by the Study Monitor. Monitoring will include source data verification (SDV) and discuss the progress of the study. SDV is confirmed by comparing completed CRFs with matched source documentation in subject's research binder. The PI will perform spot checks to verify CRFs and database entries match source documents. Verified data is entered into a computer database by the study coordinator from the completed CRF's for statistical evaluation at Thomas Jefferson University.

The monitor and/or regulatory authorities will be allowed audits at the investigation site and source data verification in which case a review of those parts of the hospital records relevant to the study may be required.

13 Quality Control and Quality Assurance

Case report forms (CRF) will be provided for the recording of all data. Data will be recorded directly and legibly onto the record forms, in blue/black ink. The signature of the investigator will attest the accuracy of the data on each CRF. If any assessments are omitted, the reason for such omissions will be noted on the CRFs. Corrections, with the reason for the corrections, should be made legibly, dated and initialed. Correction fluid is not allowed. All original data collected with paper and pen will immediately be recorded electronically by the study coordinator within the database.

Data collection and accurate documentation are the responsibility of the study staff under the supervision of the investigator. All source documents and laboratory reports must be reviewed by the study team and data entry staff, who will ensure that they are accurate and complete. Unanticipated problems and adverse events must be reviewed by the investigator or designee. The monitor and/or regulatory authorities will be allowed audits at the investigation site and source data verification in which case a review of those parts of the hospital records relevant to the study may be required.

14 Ethics/Protection of Human Participants

